## 9.5 Vital signs, physical findings, and other observations related to safety

### 9.5.1 Vital signs

Vital measurements (including SBP, DBP, PR and RR) are taken at every scheduled visit. These measurements are generally collected in standard units. If any measurements are collected in international units, they will be converted to standard units for summaries. Subject Listings will be prepared for vitals variables including absolute change from Baseline and abnormality criteria flag.

The observed value and absolute change from Baseline will be summarized (SS) descriptively by scheduled study visit, as well as Last Visit, maximum value, and minimal value. Data collected at unscheduled visits will not be included in the by-visit summary.

The number and percentage of subjects with abnormal vital signs described in Appendix 13.2 will be summarized for the overall and by 3-month interval during the Exposure Period. Subject numbers for those meeting the abnormal criteria will also be presented.

### 9.5.2 Electrocardiograms

The following ECG parameters will be recorded: heart rate, PR-interval, QRS-duration, QT-interval, QTcB [QT corrected for heart rate using Bazett's formula] or QTcF [QT corrected for heart rate using Fridericia's formula], and Investigator's conclusion on ECG profile.

The 12-Lead ECG results are collected at Entry Visit, Visit 3, Visit 5 and at visits every 6 months thereafter. An ECG at the SFU will be performed only if abnormal at EOS or EDV Visit.

For each ECG, the overall ECG result, is also collected, categorized by the investigator as one of: no abnormality, an abnormal but not clinically significant finding, or a clinically significant finding.

QTcB and QTcF will also be presented by following classification per visit:

- Observed results:  $<450\text{ms}$ ,  $450-<480\text{ms}$ ,  $480-<500\text{ms}$  and  $\geq 500\text{ms}$
- Change from Baseline:  $<30\text{ms}$ ,  $30-<60\text{ms}$ ,  $\geq 60\text{ms}$

The observed ECG parameter values and their absolute change from Baseline will be summarized (SS) descriptively for each scheduled assessment visit, as well as Last Visit, maximum value, and minimal value.

The number and percentage of subjects with no abnormality, an abnormal but not clinically significant finding, and a clinically significant finding will be summarized for each of the scheduled assessment visits. Percentages for the visit will be relative to the number of subjects with an ECG result for the visit.

The number and percentage of subjects with an abnormal ECG value described in Appendix 13.3 will be summarized for the overall and by 3-month interval during the Exposure Period. Subject numbers for those meeting the abnormal criteria will also be presented.

All 12-Lead ECG parameters will be listed per visit, including the change from baseline and a abnormality criteria flag. In addition, the data from patients with at least one finding will be listed with the finding.

### 9.5.3 Echocardiogram

Echocardiogram data are collected at Visit 2, Visit 5 and then every 3 months and at the Safety Follow-Up Visit. Only subjects who will remain in the study will have an echocardiogram at Month 24. Subjects who will taper off PSL will have an echocardiogram at the SFU Visit and at 6 months after the last dose of PSL. The data of the follow-up echocardiogram after 6 months will be obtained after data base lock and therefore analyzed separately.

Depending on the availability of data, echocardiogram abnormalities (Left Ventricle, Left Atrium, Right Ventricle, Right Atrium, Pericardium, Pulmonary Artery Systolic Pressure and overall assessment) will be summarized by each scheduled visit and by the number and percentage of subjects with an abnormality. Echocardiogram Valvular abnormality grade (Aortic Valve, Mitral Valve, Tricuspid Valve, Pulmonary Valve) described in Appendix 13.4 will be summarized descriptively. Valvular abnormality grade equal or larger than grade 2 is corresponding to valvular abnormal. Subject numbers with abnormality for any assessment will be provided.

### 9.5.4 Other safety variables

#### 9.5.4.1 Changes in CIWA-B

Subjects are tapered off study medication if they discontinue the study or complete it without continuation of PSL treatment. As part of monitoring of subjects for withdrawal symptoms during the Taper Period, the CIWA-B evaluation is performed at the EOS/EDV Visit, at the end of the Taper Period, and at the Safety Follow-Up Visit. The CIWA-B questionnaire contains 17 questions and 3 observations, which are utilized to determine the type and the severity of withdrawal symptoms, ranging from mild, moderate, severe and very severe withdrawal symptoms (Busto et al, 1989). Sub scores of each of the first 20 questions/observations (scores from 0-4) are summed up to a total score:

Total score	Interpretation
-------------	----------------

1-20	Mild withdrawal
21-40	Moderate withdrawal
41-60	Severe withdrawal
61-80	Very severe withdrawal

In case there is any sub score missing, no total score can be calculated.

There are additional two items for sleeping duration and time to fall asleep, but both are not considered in the score.

Data listings will be provided.

#### **9.5.4.2 The Columbia-Suicide Severity Rating Scale (C-SSRS)**

The C-SSRS questionnaire is self-administered by the subject and assessed by trained study personnel. This scale is used to assess suicidal ideation and behavior at Entry Visit, and at each subsequent study visit. C-SSRS data will be provided in subject listing for subjects with suicidal ideation and suicide behavior.

#### **9.5.4.3 Physical Examination**

At Entry Visit the full Physical Examination is performed. The brief Physical Examination including the body weight measurement is performed at Visit 3, Visit 5 and at each visit thereafter. The body weight is not collected at End of Taper Visit. Findings that are considered clinically-significant changes will be recorded as AEs.

Data from the Physical Examination are only provided in subject data listings displaying all data collected for all subjects by subject and visit. No summaries will be provided.

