12.3 Planned safety analyses

All safety variables will be analyzed by descriptive methods and listed on the SS.

Treatment-emergent AEs will be summarized by study period (Evaluation, Taper, and SFU) and reported for cumulative 3-month time intervals and categories of total duration of exposure, using the Medical Dictionary for Regulatory Activities (MedDRA[®]) primary System Organ Class (SOC) and Preferred Term in incidence tables. Separate tables will be provided for AEs leading to withdrawal from the study and SAEs overall and by the subcategories listed above.

Laboratory values, ECG data (heart rate, PR interval, QTcB, QTcF, and QRS interval), vital signs, and weight will be summarized by period and visit (actual values and change from Entry Visit). Possible clinically significant treatment-emergent abnormalities for laboratory values,

vital signs, and weight will be listed and summarized by period and visit. Electrocardiogram abnormalities will also be listed by period and visit.

Summary tables (and graphical outputs if needed) will be performed on the Doppler echocardiography data.

Physical and neurological examinations, psychiatric assessments and the withdrawal symptoms using the CIWA-B assessment will be provided as listing by period and visit (actual values and change from Entry Visit). The C-SSRS results will be displayed in a listing.

Any additional listings or tabulations will be described in the SAP.

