### 13.2 VITAL SIGN ASSESSMENTS - ABNORMAL

Abnormality criteria to be applied in the assessment of vital signs parameter values are given below.

PARAMETER	AGE RANGE	ABNORMALITY CRITERIA
Pulse Rate (beats/minute)	<6m	<100 >180
	6m - <3y	<90 >150
	3y - <12y	<60 >130
	12y - <17y	<50 >120
	≥17y	<50 and a decrease from Baseline of ≥15 >120 and an increase from Baseline of ≥15
Systolic Blood Pressure (mmHg)	<6m	<60 >100
	6m - <3y	<70 >120
	3y - <12y	<80 >140
	12y - <17y	<90 >160
	≥17y	≤ 90 and a decrease from Baseline of ≥20 ≥ 180 and an increase from Baseline of ≥20
Diastolic Blood Pressure (mmHg)	<6m	<40 >65
	6m - <3y	<45 >75
	3y - <12y	<50 >80
	12y - <17y	<50 >105
	≥17y	<50 and a decrease from Baseline of ≥15 >105 and an increase from Baseline of ≥ 15
Respiratory Rate (breaths/minute)	<6m	<25 >55
	6m - <3y	<20 >45
	3y - <12y	<15 >35
	≥12y	<10 >25
Body Weight	1m - <17y	<3% or 97% of the normal body weight growth curve ranges based on gender and the age of subject on date of weight assessment a

---

PARAMETER	AGE RANGE	ABNORMALITY CRITERIA
	≥17y	≥ 10% change from Baseline (an increase or a decrease) a

Abbreviations: m = month, y = year. A month is defined as 30 days; a year is defined as 365.25 days.

asource: <http://www.cdc.gov/growthcharts/>

This document cannot be used to support any marketing authorization application and any extensions or variations thereof.

REDACTED COPY

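### The SAP drops the by-visit body weight summary planned in protocol 12.3, and conflicts with its own Appendix 13.2 on whether 10% weight changes are counted

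*SAP*

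**What the plan says.** **Protocol 12.3 (Planned safety analyses).** Weight is grouped with laboratory values, ECG data and vital signs: "vital signs, and weight will be summarized by period and visit (actual values and change from Entry Visit". Possible clinically significant treatment-emergent abnormalities get the same treatment: "vital signs, and weight will be listed and summarized by period and visit". A later paragraph of the section deals with examinations: "Physical and neurological examinations, psychiatric assessments and the withdrawal symptoms using the CIWA-B assessment will be provided as listing by period and visit". So in the protocol's analysis plan weight is a summarized measurement, and examination findings are listed.

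**SAP 9.5.4.3 (Physical Examination).** "The brief Physical Examination including the body weight measurement is performed at Visit 3, Visit 5 and at each visit thereafter". The next paragraph reads "Data from the Physical Examination are only provided in subject data listings displaying all data collected for all subjects by subject and visit" and is followed by a flat statement that there will be no summaries.

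**SAP 9.5.1 (Vital signs).** "Vital measurements (including SBP, DBP, PR and RR) are taken at every scheduled visit". The section plans observed values and change from Baseline by scheduled visit. It also plans the number and percentage of subjects meeting the Appendix 13.2 criteria, overall and by 3-month interval of the Exposure Period.

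**SAP Appendix 13.2.** The table of vital sign abnormality criteria has a body weight row. For subjects aged 17 years or more the criterion is at least a "10% change from Baseline (an increase or a decrease").

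**SAP 3.9 (Changes to protocol-defined analyses).** The entries cover the onsite-setting column, the COVID-19 eCRF and impact listing, the China region, AED drug load and the Japan addendum. Weight is not among them.

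**The concern.** The study's primary objective is long-term safety, and weight is a safety variable in both documents (protocol 4.1.2; SAP 2.2.1.2). It is scheduled repeatedly over about two years so that a drift can be seen. A gradual change in a group shows in means and changes by visit and is hard to see in subject listings. A programmer following SAP 9.5.4.3 would produce no such table.

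The 10% criterion raises a second problem. One section asks for a count of subjects meeting it and another rules out any summary of the data it is applied to. Whether the study report contains that count then depends on which section the programmer reads first. The same uncertainty carries into the Japan and non-Japan repeats, because SAP section 15 repeats every table described in the SAP.

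**Working it through.** No sample size, power or precision figure is involved, so the check is a comparison of texts.

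**1. By-visit values and change**

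| Source | Instruction for weight |
|---|---|
| Protocol 12.3 | Summarize by period and visit, actual value and change from Entry Visit |
| SAP 9.5.4.3 | Weight sits in the brief examination; listings only, no summaries |
| SAP 9.5.1 | Weight not named |
| SAP 6.1 | Weight at parent-study entry only, as a demographic |

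The protocol plans the table and no SAP section does.

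**2. Count of subjects with at least 10% change**

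| Source | Instruction |
|---|---|
| Protocol 12.3 | List and summarize by period and visit |
| SAP 9.5.1 with Appendix 13.2 | Number and percentage, overall and by 3-month interval |
| SAP 9.5.4.3 | No summaries |

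Here the SAP conflicts with itself. It is not a clean omission.

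**3. Does SAP 9.5.1 cover weight without naming it?** The sentence quoted from 9.5.1 describes measurements made at every scheduled visit. Weight is not measured at every visit. The schedule (protocol Table 5-1, SAP Table 2-1) has no weighing at Visit 2, Visit 4 or End of Taper, and SAP 9.5.4.3 confirms the last of these. Footnote f of both tables defines vital signs as pulse rate, respiratory rate, systolic and diastolic pressure. Weight has its own row.

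**4. How many weighings are affected?** Scheduled weighings are Visit 1, Visit 3, Visit 5, Visits 6 to 11, EOS or EDV, and SFU: 1 + 1 + 1 + 6 + 1 + 1 = 11 at most. The Visit 1 value comes from the parent study, and SFU applies only to subjects who stop padsevonil, so many subjects will have fewer.

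**5. Does the default rule help?** SAP section 1 applies the protocol analysis unless the SAP specifies otherwise. On its ordinary reading 9.5.4.3 does specify otherwise.

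**6. Is the change declared?** Not in SAP 3.9. The Amendment 1 log in SAP 14.1 records moves to listings for CIWA-B, psychiatric status, SSG, QOLIE-31-P, HADS and TSQM-9, and has no entry for weight.

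**7. Reference point.** Protocol 12.3 takes change from the Entry Visit. SAP 9.5.1 and Appendix 13.2 use Baseline, which SAP 3.3 defines as that of the parent study unless noted otherwise. Adding weight to 9.5.1 without comment would therefore still depart from the protocol.

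**The case against.** A coherent reading of the SAP is possible. Appendix 13.2 classes weight as a vital sign parameter. The list in 9.5.1 is introduced by a word that need not be exhaustive. The exclusion of summaries in 9.5.4.3 may be meant for examination findings, as the matching sentence in 9.5.4.4 is for neurological findings. On that reading 9.5.1 would give both the by-visit table and the count, and where the SAP is unclear the protocol governs. The grouping of weight with physical examination also comes from the protocol itself (4.1.2 and 9.3.4).

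This shows how the conflict probably arose, but it does not remove it. Section 9.5.1 speaks of measurements at every scheduled visit, footnote f limits vital signs to four parameters, and 9.5.4.3 expressly includes the weighing. Reading the exclusion in 9.5.4.3 narrowly still leaves no SAP text that names weight for a by-visit summary.

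Three parts of the objection do stand. Clinically significant changes found at examination are recorded as adverse events and so enter the TEAE tables. All weights stay in the listings, and SAP 3.1 provides for calculated change there. A study terminated early may reasonably want fewer tables, provided the reduction is declared.

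**Conclusion.** Following the SAP as written, the by-visit weight summary planned in the protocol is lost, the 10% count is both called for and excluded, and neither is declared as a change. This should be corrected, but its weight is modest. The affected item is one of the other safety variables, inside an entry for physical examination; the primary safety variables are TEAE incidence and TEAEs leading to withdrawal.

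Two stronger readings are tempting and not supported. A reader might infer that the study would have no group-level result on weight at all. The Appendix 13.2 count is arguably required by 9.5.1, and clinically significant changes reach the adverse event tables, so what is clearly lost is the by-visit value and change. A reader might also size the loss from the planned enrollment of about 1000 subjects. SAP 3.9 records early termination and a COVID-19 effect on enrollment, and the documents give no actual number and no expected rate of weight change. A precision figure would rest on assumptions, and the point does not need one.

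The conclusion assumes that the data referred to in 9.5.4.3 include the weighing, as that section's own description of the brief examination indicates. If they do not, the internal conflict over the count disappears, but the missing by-visit summary remains.

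**What to change.** 1. In SAP 9.5.1, name body weight as a parameter. Plan observed value and change at the visits where weight is scheduled, and the number and percentage meeting the Appendix 13.2 criterion, overall and by 3-month interval. Showing gains and losses of at least 10% separately is preferable, since Appendix 13.2 pools opposite directions, but this is a refinement and not something the protocol requires.
2. State the reference for change in weight: the Entry Visit, as in protocol 12.3, or parent-study Baseline with the departure entered in SAP 3.9.
3. In SAP 9.5.4.3, limit the listing-only and no-summary sentences to examination findings.
4. If dropping the weight summaries was intended, say so in SAP 3.9 and delete the body weight row from Appendix 13.2.

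The cost is a few sentences and one more parameter in tables that are already planned. The data are already scheduled for collection.

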#### **9.5.4.4 Neurologic Examination**

At Entry Visit the full Neurological Examination is performed. The brief Neurological Examination is performed at Visit 3, Visit 5 and at each visit thereafter. Data from the Neurological Examination are collected on the Neurological Examination Complete and Neurological Examination Brief CRFs Findings that are considered clinically-significant changes will be recorded as AEs.

A brief neurological examination will include general assessment and the evaluation of reflexes, muscle strength and coordination, and cerebellar function.

Data from the Neurological Examination are only provided in subject data listings presented by subject and visit, displaying all data collected for all subjects. No summaries will be provided.

#### **9.5.4.5 Changes in Psychiatric and Mental Status**

The Psychiatric and Mental Status is performed at Entry Visit, Visit 3, Visit 5 and at each visit thereafter. These data are collected on the Psychiatric and Mental Status CRF. Assessment of specific domains of psychiatric and cognitive symptoms will be performed by a staff member

trained in the identification of psychiatric symptoms. The parameters to be evaluated are orientation, attention, memory, mood, and calculus.

For each of these assessments, data is provided in subject data listings presented by subject and visit, displaying all data collected for all subjects

There are no derived outcomes for the Psychiatric and Mental Status evaluation and no imputation rules for missing response values and no date imputation rules are applicable.

## 10 EFFICACY ANALYSES

Analyses of efficacy endpoints will be performed on the FAS.

### 10.1 Statistical analysis of the primary efficacy variables

#### 10.1.1 Derivations of primary efficacy variable

Seizure frequency (SF) refers to the 28-day adjusted seizure frequency, which is defined as:

$$SF = (\text{Number of Seizures}) \times (28 / D)$$

- where Number of Seizures = total number of seizures during an analysis period or time interval. For cluster seizures, the number of cluster episodes will be included.
- D = number of days for which the diary was available during the analysis period or time interval.

Change from Baseline in seizure frequency will be calculated as seizure frequency during an analysis period or time interval minus the Baseline seizure frequency.

The primary efficacy variable is the change from Baseline in the observable focal-onset seizure frequency over the Evaluation Period.

#### 10.1.2 Primary analysis of the primary efficacy variable

The observed and the absolute change in 28-day adjusted observable focal-onset seizure frequency will be summarized (FAS) for the overall Evaluation Period. The summary will be repeated for each region. A per-subject listing (FAS) will be provided with details of seizure diary including type of seizure, cluster, number of seizures per diary. No additional statistical testing or modelling will be performed.

### 10.2 Analysis of other efficacy variables

Other efficacy variables are listed in [Section 2.2.2.2](#).

## 10.2.1 Derivations of other efficacy variables

This section describes variable derivation and calculation of descriptive statistics to be used for analyses.

### 10.2.1.1 Percent reduction in seizure frequency from Baseline of parent study

The percent reduction in seizure frequency (PRD) from the Baseline is defined as:  $PRD = [(SFB - SFT) / SFB] \times 100$ , where SFT corresponds to the 28-day adjusted seizure frequency during an analysis period or time interval and SFB corresponds to the Baseline seizure frequency. A negative PRD indicates an increase in seizure frequency from Baseline of parent study.

### 10.2.1.2 50%, 75% and 90% Responder

Responder status (yes or no) of a subject is determined by the percent reduction in seizure frequency (PRD) from Baseline of parent study. A subject is defined as a XX% responder if s/he has a reduction in seizure frequency (PRD) of at least XX% from the Baseline. The XX% responder rate (RR) will be calculated as the proportion of XX% responders.

### 10.2.1.3 Seizure-free status (Yes or No)

Subjects will be considered seizure-free for a given period or time interval if the subject, completes the period, reports zero seizures during the period, and has no more than 10% of days in the period for which seizure data is not available (ie, "Not Done" is reported on the Seizure Count CRF).

### 10.2.1.4 Number and percentage of Seizure-free days

The number of seizure-free days will be the total number of days within an analysis period or time interval for which daily diary data was available and indicated that no seizures occurred. The percentage of seizure-free days will be computed as 100 times the number of seizure-free days divided by the number of days for which daily diary data was available. Days without the corresponding daily diary data will not be used in these computations.

### 10.2.1.5 Seizure Severity Global Item (SSG) variables

The SSG consists of 2 items from the Seizure Severity Questionnaire and asks the subjects to evaluate the severity of their seizures for the last 4 weeks. The subject describes all seizure types when answering the questions. Seizure Severity will be asked for Entry Visit, Visit 5, and every 3 months thereafter until EOS/EDV Visit at the beginning of each visit. The seizure-intensity during the last 4 weeks is collected on a 7-point scale with 7 = very severe and the assessment of change since starting IMP, is also collected on a 7-point scale with 7 = much worse.

### 10.2.1.6 QOLIE-31-P

The QOLIE-31-P assesses subject functioning and health-related quality of life. The QOLIE-31-P (Cramer et al, 2003) is an adaptation of the original QOLIE-31 instrument (Cramer et al, 1998) that includes 31 items grouped into 7 multi item subscales (Seizure Worry [5 items], Overall Quality of Life [2 items], Emotional Well-being [5 items], Energy/Fatigue [4 items], Cognitive Functioning [6 items], Medication Effects [3 items], and Daily Activities/Social Functioning [5 items]) and 1 health status item.

In addition to the 31 items of the QOLIE-31, the QOLIE-31-P contains 7 items assessing the degree of “distress” associated with the topic of each subscale (ie, distress items) and 1 item asking about the relative importance of each subscale topic (ie, prioritization item).

The QOLIE-31-P will be completed at Visit 6 and 6 months thereafter. It is provided to each subject at the beginning of the visit. The subject completes the questionnaire on his/her own. The Investigator or designee will verify that all questions have been answered. Further details about the QOLIE-31-P are provided in the scoring manual.

